# STATISTICAL SIGNIFICANCE

We use a statistical significance level of  $\alpha$  < 5%.

#### **VI: DATA SAFETY**

The project will be registered with the North Denmark Region and all sensitive data will be stored on the secure servers of Aalborg University Hospital or in a REDCap database administrated by this institution and in accordance with the Data Protection Act (*databeskyttelsesloven*). All stored data will be anonymized after termination of the project. No data will be given over to a third party.

# **VII: STUDY LIMITATIONS**

Due to the study's single-center nature, our findings may not be applicable to the entire population of acromegalic patients.

# **VIII: ETHICAL CONSIDERATIONS**

#### A. INFORMED CONSENT

The initial inquiry about participation of patients with acromegaly will be made by one of two specialists in pituitary endocrinology. Potential participants will receive both oral and written information

(*"Deltagerinformation"* and *"Før du beslutter dig"*). Further information will later be given, by the principal investigator or another member of the research team, and will include details about the tests involved:

- This is a scientific project designed to investigate the optimal method for diagnosing acromegalic osteopathy, as well as testing balance and strength
- Information regarding the included examinations, including the risk of minimal to moderate pain associated with the BMSi measurement and the minimal exposure to ionizing radiation associated with HR-pQCT and DXA scans
- Information and separate consent regarding the creation of a biobank consisting of participants' blood samples, which will be stored for future analysis, but no more than 15 years after completion of the study. A renewed application will be submitted to the regional ethics committee in case the research team should wish to analyze the blood samples in the future. Prior to analysis, the Danish Tissue Utilization Register (Vævsanvendelsesregistret) will be consulted; should the participant be listed herein, the blood sample will not be analyzed.
- That withdrawal of consent, and as such withdrawal from participation, is possible at any time and with no given notice or explanation
- That collected data will be published in anonymized form with no possibility of being traced to the participant
- That collected data will be securely stored in accordance with the rules in place
- That at least 24 hours are given to deliberate before providing informed consent
- That potential participants have the right to bring a relative or other representative to the informational meeting

Potential participants are given at least 24 hours to deliberate, before any consent form is signed.

The project will be performed in compliance with the ICH GCP and the Helsinki Declaration for biomedical research involving human test subjects. The study will be subject to continuous internal quality monitoring, in accordance with GCP guidelines.

The project will be prospectively registered with www.clinicaltrials.gov.

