Studies concerning balance and falls among acromegalic patients remain scarce. Thus far, it has been suggested that acromegalic patients have impaired balance and postural control, due to factors such as alterations in body composition, enthesopathy, myopathy, arthropathy or visual field disturbances. Indeed, altered body composition has been demonstrated in acromegalic patients using whole-body DXA scans and reduced peripheral muscle strength has been found using hand grip strength (HGS) as a measure. Moreover, an increased fear of falling has been observed in patients with acromegaly, although the frequency of falling seems to be similar to healthy controls. However, fall risk, as evaluated via the timed up-and-go (TUG) test, has been shown to be increased in acromegalic patients. An improvement in several dynamic balance parameters, as evaluated by stabilometry, has been demonstrated among acromegalic patients after a relatively short training program, indicating a potential benefit of focused physical therapy for this patient group. Given that acromegalic patients have impaired bone quality, preventing falls may be of considerable clinical relevance. However, this subject calls for further investigations. To our knowledge, no studies have directly compared body composition and dynamic muscle parameters such as hand grip strength, leg extension strength, timed up-and-go and stabilometry in acromegalic subjects.

Acromegaly-related osteopathy has been a subject of interest in recent years, as it has been established that patients with acromegaly have increased bone turnover, reduced bone quality and an increased risk of fractures despite normal bone mineral density as assessed by DXA-scans. Secondary hypogonadism due to tumor mass effect or pituitary surgery plays a significant role in the diminished bone quality of acromegalic patients, even after disease control is achieved.

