Although normal or even increased cortical bone thickness has been reported using iliac crest bone biopsies, hip structure analysis and high-resolution cone beam tomography, other cortical bone parameters such as bone material strength index (BMSi) have been shown to be reduced, even in wellcontrolled acromegalic patients, suggesting compromised bone fracture resistance in acromegalic patients. Decreased BMSi, as measured by micro-indentation using an OsteoProbe, has been shown to be correlated with fragility fractures in postmenopausal women and in individuals with diabetes. Only one study has measured BMSi on acromegalic subjects and found significantly lower values compared to healthy controls, regardless of biochemical control, hypogonadism or presence of vertebral fractures. If and how BMSi values correlate to reduced bone quality, as assessed by HR-pQCT, remains to be examined in patients with acromegaly. Thus far, no studies exist regarding the integration of HR-pQCT-derived bone parameters, BMSi and the presence of vertebral fractures. By combining these diagnostic modalities, we aim to perform an integrated assessment of bone quality in acromegalic patients, examining both the cortical and trabecular bone compartments to further our understanding of acromegalic osteopathy. This may provide more insight into which diagnostic modality is optimal as a measure of fracture risk in acromegalic patients, since standard DXA scans have proved less useful in this regard.

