#### C. OBJECTIVES

Aim:

A. To perform a comprehensive, integrated assessment of balance, bone and joint quality, body composition, muscle strength, fear and risk of falling and fracture risk of acromegalic patients.

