# STATISTICAL METHODS

Statistical testing will be performed using STATA® version 17 for Mac (StataCorp LLC, Texas, USA).

Data will be summarized using descriptive statistics such as frequency, percentage, mean and standard deviation. Statistical testing will be applied to compare acromegalic subjects to healthy controls, including t-tests, chi-squared tests and Mann-Whitney U tests, where applicable.

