# C. BENEFITS TO SUBJECTS

The participants will not benefit directly from participation in this study. However, as we aim to examine the optimal means of diagnosing acromegalic osteopathy, our findings may contribute to earlier detection of this condition. This is of potential future benefit for patients with acromegaly, as early diagnosis and treatment may prevent fractures, and thus save patients considerable morbidity. Identifying patients at risk for falling will enable treating physicians to implement relevant measures to prevent falls, and thus, potentially prevent fractures. Should HR-pQCT prove valuable in the diagnosis of acromegalic arthropathy, this may also be beneficial to patients in the future.

As such, the potential future benefits to patients with acromegaly are deemed sufficient justification for performing the study.

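### Does describing the study as a search for the optimal diagnostic method require a within-patient analysis that the plan does not name?

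*Combined protocol and SAP*

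**What the plan says.** The diagnostic purpose appears in three places, with differing strength.

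- VIII.A Informed consent, in the list of points given to participants: "This is a scientific project designed to investigate the optimal method for diagnosing acromegalic osteopathy, as well as testing balance and strength".
- VIII.C Benefits to subjects: "we aim to examine the optimal means of diagnosing acromegalic osteopathy". Fall risk and arthropathy are cited there as further possible benefits, and the section says that participants gain nothing directly.
- II.B, in the background: "This may provide more insight into which diagnostic modality is optimal as a measure of fracture risk in acromegalic patients", followed by the reason "since standard DXA scans have proved less useful in this regard". The same paragraph raises a question within patients: "If and how BMSi values correlate to reduced bone quality, as assessed by HR-pQCT, remains to be examined in patients with acromegaly".

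The formal aim in II.C is broader and names no diagnostic comparison. It begins "To perform a comprehensive, integrated assessment of balance, bone and joint quality". The hypothesis expects impaired bone quality, impaired balance and more falls risk in patients, and adds that combining modalities will help in understanding mechanisms.

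The analysis text in V.A reads: "Statistical testing will be applied to compare acromegalic subjects to healthy controls, including t-tests, chi-squared tests and Mann-Whitney U tests, where applicable". The sample size calculation concerns the patient-control difference in trabecular density. III.D says in general terms that suitable analyses will be used. No correlation, ROC analysis or comparison of patients with and without fracture is named, and no reference standard for osteopathy is defined.

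**The concern.** A study that sets out to find the best way of diagnosing a condition normally needs a reference standard and an analysis of each method against it among people who have, or may have, the condition. This plan names neither. Comparing patients with controls shows which measures differ in acromegaly. It does not show whether microindentation (BMSi) and HR-pQCT rank patients alike, or which of them tracks vertebral fracture.

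Two things would be at stake. First, participants accept microindentation and low-dose radiation partly on the strength of a purpose that the named tests do not serve. Second, if within-patient analyses are added once the data are in hand, the HR-pQCT parameter and site are free choices, and a chance correlation could be reported as a finding. The data needed (HR-pQCT, BMSi, DXA, vertebral fracture assessment, fracture history) come from the same patients, so the omission looks easy to avoid.

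**Working it through.** **1. Is the plan coherent for what it formally sets out to do?** Inputs from V.A: means 180 and 150, SD 40, significance level 5% (two-sided assumed), 28 per group.

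- n per group = 2 × (1.960 + 0.842)² × 40² / 30² = 2 × 7.849 × 1.778 = 27.9, so 28.
- Power at 28 per group: 80.1% by the normal approximation and 78.7% by the noncentral t. At the planned 30 per group (III.B): 82.8% and 81.5%.

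The stated 80% reproduces. It belongs to the patient-control comparison, which is also what the first part of the hypothesis and the named tests address.

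**2. Do patient-control tests bear on the diagnostic question at all?** Partly. II.B describes the bone disease as "reduced bone quality and an increased risk of fractures despite normal bone mineral density as assessed by DXA-scans". If so, finding which of DXA, HR-pQCT and BMSi differ between patients and controls says something about which methods register the disease. It leaves open how they relate to one another among patients.

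**3. Are within-patient analyses ruled out?** No. The word *including* in V.A makes the list of tests illustrative, and III.D is open as well. II.B states the BMSi to HR-pQCT question directly, so an analyst who follows the protocol has good reason to examine it.

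**4. What would naming such analyses deliver with 30 patients?** The documents give no fracture count, so 6, 10 or 15 of 30 are assumed. With A = 0.75, Q1 = A/(2 − A) = 0.600 and Q2 = 2A²/(1 + A) = 0.643, the Hanley-McNeil formula is

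SE² = [A(1 − A) + (n1 − 1)(Q1 − A²) + (n0 − 1)(Q2 − A²)] / (n1·n0).

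- 6 fractures, 24 without: (0.1875 + 5 × 0.0375 + 23 × 0.0804)/144 = 0.01544; SE 0.124; half-width 1.96 × 0.124 = 0.24; interval 0.51 to 0.99.
- 10 and 20: SE 0.101, half-width 0.20.
- 15 and 15: SE 0.090, half-width 0.18.

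For two methods with assumed AUCs of 0.80 and 0.70, SE of the difference = √(SE1² + SE2² − 2r·SE1·SE2). With r between the estimates assumed 0 to 0.5, it runs from 0.174 (6 fractures, r = 0) to 0.090 (15 fractures, r = 0.5). Power is then about 9% to 20%.

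For a Spearman correlation of 0.4 with n = 30: z = 0.424, SE = √[(1 + 0.4²/2)/27] = 0.20, z limits 0.032 and 0.816, so 0.03 to 0.67 on the correlation scale. On the usual Fisher z approximation for a correlation, the smallest value detectable with 80% power is tanh(2.802/√27) = 0.49.

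**5. How large is the risk from free choice?** III.D names six HR-pQCT parameters at two sites, so 12 BMSi correlations are possible. If all were tested at 5% and independent, the chance of at least one false positive would be 1 − 0.95¹² = 46%. By simulation it falls to about 23% if the tests are correlated at 0.7. With four correlations the corresponding figures are 19% and 13%. The plan describes no such set of tests, so these figures show what misuse would cost and not what the plan does.

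**The case for a change.** The strongest case for a change is that it is cheap. A short exploratory paragraph and a softer word in VIII.A and VIII.C would bring the stated purpose into line with the analysis, need no new data, and limit selective reporting. VIII.C also rests the justification of the study on its future benefits, and better diagnosis comes first among them.

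Much of this is accurate. *Optimal* is a strong word for a study of this size, no within-patient analysis is named, and an open list gives no protection against choosing parameters afterwards. A very large gap between methods might even be visible: a binormal simulation with the DeLong test gives 46% to 94% power for AUCs of 0.80 against 0.50 (6 to 15 fractures, correlation between methods 0 to 0.7, all assumed).

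It does not carry through to a change, for four reasons.

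- The strong wording stands in the ethics section and not in the aim or hypothesis. To investigate or examine a question is not to promise a ranking of methods, and the background is already hedged.
- The harm depends on analysts either skipping the correlation that II.B raises or searching many and reporting one. The documents suggest neither.
- Which correlations, which fracture definition and which sites to name are matters of preference. Competent statisticians would choose differently, and none of the choices would identify an optimal method at these numbers.
- The participant leaflet itself is not in the documents, so how it words the purpose cannot be judged. III.D sets recruitment from December 2022 to March 2025, and rewording cannot reach people already informed.

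**Conclusion.** No change follows. The gap is one of missing exploratory detail, together with an ambitious word in the ethics section. Carried out as written, the plan gives a sound patient-control comparison, with its stated power reproduced at 80.1% (78.7% by the noncentral t). Within-patient analyses remain open to the analysts, who have both the data and a stated question to guide them. Any such result would be exploratory whether or not it was listed beforehand. The AUC half-width is 0.18 to 0.24 at an AUC of 0.75, and the interval for a correlation of 0.4 runs from 0.03 to 0.67.

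The sample-size check uses only the protocol's figures and a two-sided 5% level. The AUC, paired-comparison and false-positive figures rest on assumed fracture counts, AUCs and correlations, and are illustrative. The conclusion does not depend on their exact values. It would be different if a diagnostic comparison were the formal aim, or if the plan excluded within-patient analyses, and neither is the case.

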# B. RISKS AND SIDE EFFECTS

All methods used have been tested in previous studies with no side effects being reported. The risks associated with the above-mentioned procedures are limited as only low-dose radiation is used, and all measures are taken to ensure sterility when relevant.

No changes in the participants' regular medication will be made, and no new medication will be administered, except for local anaesthetics given during the BMSi measurement.

The main side effect that may be anticipated is pain in relation to the BMSi measurement, however relevant measures will be taken to counter this, and the pain is transient. Aside from this, there is a minimal amount of ionizing radiation from HR-pQCT and DXA scans, as mentioned above.

These are the anticipated side effects related to each examination included in the protocol:

- *Blood samples*: minimal risk of infection; disinfectant will be applied before skin puncture. Risk of small hematoma around the puncture site.
- *HR-pQCT scan*: low dose of ionizing radiation (0,003 0,005 mSv). Mild discomfort from sitting still during the scan.
- *Whole body, hip and spine DXA and VFA*: low dose of ionizing radiation (0,007 0,043 mSv).
  - Theoretically, the radiation doses associated with the HR-pQCT and DXA scans may increase the life-time risk of cancer from approximately 25% to less than 25,000003 %.
- *Microindentation (BMSi measurement)*: mild to moderate pain/discomfort related to administration of local anaesthesia. Mild to moderate pain when contact is made between the probe and the periosteum; local anaesthesia will be administered to alleviate this. Minimal risk of infection after skin puncture; the procedure will be performed under sterile conditions to minimize this risk.
- *TUG, stabilometry, hand grip strength, leg extensions, nerve conduction test, visual examination*: no side effects or risks expected.

As all the procedures are associated with a low risk of lasting side effects or complications, and the results of the study are expected to contribute to improved diagnosis and treatment of debilitating conditions in the future, the investigators consider the study procedures ethically responsible.

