# HIGH RESOLUTION PERIPHERAL QUANTITATIVE COMPUTED TOMOGRAPHY (HR-PQCT)

HR-pQCT is a 3-dimensional imaging modality that can be applied to bone and joints *in vivo*, in order to non-invasively assess the quantity and quality of trabecular and cortical bone compartments separately. HR-pQCT will be applied to peripheral skeletal sites, namely the distal radius and tibia, where image slices equivalent to 9 mm of bone will be acquired. From this, parameters such as volumetric bone mineral density (vBMD), cortical density, cortical porosity, trabecular density, trabecular thickness, trabecular spacing and others will be calculated using specialized software. In the same scanning session, images of the wrist and ankle joints will be produced and analyzed for features of arthrosis, such as erosions, osteophytosis and others.

The scanner's gantry is relatively narrow and shallow (rear physical stop) only allowing the distal peripheral skeleton to be accommodated. The limb being scanned is immobilized in a carbon fiber shell. A scout view, essentially a two-dimensional x-ray scan, is obtained so that the operator can identify a precise region for the three-dimensional measurement. Because HR-pQCT uses a polychromatic X-ray source it is subject to beam hardening as well as scatter artefacts, which can significantly impact geometric and densitometric measures. Once the images have been acquired, a default patient evaluation protocol is used to analyze the scans over the entire 9 mm three-dimensional region to assess a wide range of standard and optional structural and density parameters.

The effective radiation dose for one HR-pQCT scan at the distal tibia or radius is 0,003 – 0,005 mSv, which is considered a low radiation dose. In comparison, a regular chest X-ray yields a dose of 0,01 – 0,1 mSv and dental X-ray yields 0,005 mSv. The worldwide average effective radiation dose from natural background radiation is 2,4 mSv per year. The average effective radiation dose in Denmark is 3 mSv per year.

Estimated time: 30 min.

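### Does the risk section understate the HR-pQCT radiation dose by listing one scan beside a DXA total?

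*Combined protocol and SAP*

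**What the plan says.** Section VIII.B introduces its list with "These are the anticipated side effects related to each examination included in the protocol". The HR-pQCT entry is labelled as a scan, in the singular, and gives "low dose of ionizing radiation (0,003 0,005 mSv). Mild discomfort from sitting still during the scan"; the dash between the two numbers was lost when the text was extracted. The entry after it names whole body, hip and spine DXA together with VFA and gives 0.007 to 0.043 mSv.

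The basis of each figure is in section III.D. The HR-pQCT subsection says "The effective radiation dose for one HR-pQCT scan at the distal tibia or radius is" 0.003 to 0.005 mSv. It also says "HR-pQCT will be applied to peripheral skeletal sites, namely the distal radius and tibia", and adds: "In the same scanning session, images of the wrist and ankle joints will be produced". The DXA subsection lists its component doses and sums them to 0.007 to 0.043 mSv. No section sums the HR-pQCT scans or combines the two modalities.

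The general statements that draw on these figures are qualitative. Section VIII.B says "The risks associated with the above-mentioned procedures are limited as only low-dose radiation is used", and section VIII.A says participants will be told of "the minimal exposure to ionizing radiation associated with HR-pQCT and DXA scans".

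**The concern.** Two adjacent entries in one list are on different bases. The HR-pQCT figure covers one scan at one site, and the DXA figure covers every DXA and VFA scan a participant has. Neither entry states its basis in words. A reader of the list alone could take both as the exposure from the whole examination and so count half of the planned HR-pQCT minimum.

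What would be at stake is the account of risk given to the ethics committee and to participants. Participants have no direct benefit from the study (section VIII.C), and its acceptability rests partly on the radiation dose being low. If the true total were large enough to put that description in doubt, the section would need correcting.

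**Working it through.** All inputs are the protocol's own figures, with decimal commas written as points. Lower ends are added to lower ends and upper ends to upper ends.

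**Inputs**
- HR-pQCT, one scan at one site: 0.003 to 0.005 mSv (III.D, HR-pQCT).
- Bone sites scanned: 2, distal radius and distal tibia (III.D, procedures overview and HR-pQCT).
- DXA whole body: 0.001 to 0.01 mSv. Hip and lumbar spine: 0.003 to 0.03 mSv. VFA: 0.003 mSv (III.D, DXA).
- Yardsticks: "The average effective radiation dose in Denmark is 3 mSv per year", and 0.01 to 0.1 mSv for a chest X-ray (III.D, HR-pQCT).

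**1. Reproduce the printed figures**
- DXA, lower: 0.001 + 0.003 + 0.003 = 0.007 mSv.
- DXA, upper: 0.01 + 0.03 + 0.003 = 0.043 mSv.
- Both match the DXA subsection and the risk list, so the DXA entry is a total.
- HR-pQCT: 1 × 0.003 = 0.003 and 1 × 0.005 = 0.005 mSv. The entry is reproduced as one scan at one site, and only so.

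**2. HR-pQCT over both planned sites**
- Lower: 2 × 0.003 = 0.006 mSv.
- Upper: 2 × 0.005 = 0.010 mSv.
- Beyond the printed figure: 0.003 to 0.005 mSv per participant.

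**3. Both modalities together**
- Lower: 0.006 + 0.007 = 0.013 mSv.
- Upper: 0.010 + 0.043 = 0.053 mSv.

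**4. Size against the protocol's yardsticks**
- Combined: 0.013 / 3 = 0.4% and 0.053 / 3 = 1.8% of the annual Danish dose.
- The uncounted part alone: 0.003 / 3 = 0.10% and 0.005 / 3 = 0.17%.
- The whole combined range lies within the range given for one chest X-ray.

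**5. Sensitivity to the joint images**

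The protocol does not say whether the wrist and ankle images need separate exposures. Assume, as the documents do not state, two further scans at the same dose per scan.
- HR-pQCT: 4 × 0.003 = 0.012 to 4 × 0.005 = 0.020 mSv.
- Combined: 0.012 + 0.007 = 0.019 to 0.020 + 0.043 = 0.063 mSv.
- Upper end against the annual dose: 0.063 / 3 = 2.1%, still within the chest X-ray range.

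Extra exposures can only raise the two-site sum, which is why the figures in steps 2 and 3 are minima.

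**The case for a change.** The strongest case for a change is this. The list speaks of each examination in the protocol, and the HR-pQCT examination is one session covering both sites. The DXA subsection shows that the authors meant to give totals where several scans are made. With a total in the next entry, nothing prompts the reader to double the HR-pQCT figure. Participants are owed a full statement of exposure, and the correction would cost one line.

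Part of this stands. The two entries are on different bases, the basis is not spelled out in the list, and someone who added them would fall short by 0.003 to 0.005 mSv.

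The rest does not carry it to an error in the plan. The HR-pQCT label is singular and its figure is right for one scan; the DXA label names its components and its figure is their sum. The paragraph before the list refers back to the earlier description of the radiation, where the per-scan basis and both sites are given. No stated sum is wrong. A percentage shortfall in the combined dose would be measured against an addition the protocol never makes. Section VIII.A quotes no dose, and the participant information is not in the reviewed text, so it is not known whether participants would see the single-scan figure.

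The lifetime cancer risk sentence in section VIII.B does not help either side. It refers to the scans of both modalities but shows neither its input dose nor its risk coefficient, so this check neither confirms nor faults it.

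**Conclusion.** The arithmetic behind the concern is right: with two sites, HR-pQCT exposure is at least 0.006 to 0.010 mSv, and at least 0.013 to 0.053 mSv with DXA. This is nevertheless a point of labelling, and nothing in the plan has to change. The printed dose is correct per scan, the number of bone sites is stated, and a reader can double the figure from section III.D.

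Stating the sum would alter no procedure, endpoint, sample size, analysis or safety measure. The protocol's low-dose and minimal-exposure descriptions hold at the combined upper end of 0.053 mSv, about 1.8% of the annual Danish dose. They also hold at 0.063 mSv if the joint images need two more exposures.

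The conclusion rests on the protocol's own dose per scan, on one scan at each of the two bone sites, and on no repeat scans, which the documents do not address. If the text is revised for another reason, the HR-pQCT entry could be marked as a per-scan figure, but that is an editorial choice.
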